Rate of Recovery from Strenuous Exercise in Physically Active Older Adults

NCT02899650

August 22, 2016

Study Protocol

Subjects. A total of 39 healthy men and women were studied. They were divided into three groups according to their age and physical activity status; the young sedentary group, the young exercise-trained group, and the older exercise-trained group. Young and older groups were 19-39 and 50-77 years of age, respectively. Subjects in the trained groups had been performing regular aerobic exercise (primarily running) at least twice or more a week for at least two years. The subjects in the sedentary group had not participated in a regular exercise program for at least one year. Older sedentary subjects were not included in the present study due to safety concerns associated with downhill running. All subjects were nonsmokers. Subjects were free of overt chronic diseases as assessed using medical history. All subjects were free of any physical limitations. All older women were postmenopausal. Three women in the young groups were using oral contraceptives, and other premenopausal women had been experiencing regular menstrual cycles. In premenopausal women who did not use oral contraceptives, all measurements were conducted in early follicular phase of their menstrual cycle because the phase contains the lowest estrogen levels. All subjects gave their written informed consent prior to study participation, and the ethics committee of the University of Texas at Austin approved all procedures.

Procedures. Subjects visited the laboratory on five separate occasions. On the first visit, subjects filled out the standard health research questionnaire. They then underwent a familiarization/measurement session. The familiarization portion was used to introduce the subjects to downhill running on treadmill. Then each subject's maximal oxygen consumption ($\dot{V}O_{2max}$) were measured using a maximum exercise test. On the

second visit, the subjects underwent the baseline measurements, including anthropometry, body composition, markers of muscle damage (plasma concentrations of creatine kinase and myoglobin, visual analog scale of pain and soreness, and joint range of motion) and muscular strength of their leg (maximum isometric contraction). Following the measurements, subjects performed downhill running. After the downhill running protocol, various markers of muscle damage and muscular strength were obtained 24 hours post (the third visit), 48 hours post (the fourth visit) and 72 hours post (the fifth visit). There were at least 3 days between the first and second visits, with no more than 7 days between the two visits. Subjects were instructed to fast at least 3 hours and to avoid any strenuous exercise for the 48 hours before the measurements. Subjects were asked to keep their regular diet throughout the testing sessions.

Maximal oxygen consumption. Maximal oxygen consumption ($\dot{V}O_{2max}$) was measured with an incremental treadmill protocol test as previously described [32]. After a 5-min warm-up period, the subject ran at a speed that corresponded to 70–80% of age-predicted maximal heart rate [31]. Treadmill speed remained constant throughout the test, while the grade was increased by 2% every 2 minutes until volitional exhaustion. A mouthpiece and heart rate monitor (Polar Electro Inc, Lake Success, NY) were worn to collect expired gas and obtain heart rate. The rating of perceived exertion (RPE) scale was obtained every minute. A metabolic cart was used to measure flow and gas composition from expired air collected by the mouthpiece. At least two of the following three criteria were met by each subject: 1) a plateau in oxygen uptake with increasing exercise intensity, 2) a respiratory exchange ratio ≥ 1.1 , and 3) achievement of age-predicted maximal heart rate [31]. $\dot{V}O_{2max}$ was determined by the highest values

of oxygen uptake that were sampled every 20 s. The $\dot{V}O_{2max}$ values were used to set the speed of treadmill during the downhill running.

Downhill running. Subjects performed downhill running at -16% of slope at a speed that corresponded with 65% of their $\dot{V}O_{2max}$ [26]. Subjects warmed up on treadmill on a level grade at the same speed as downhill running for 5 min. Following the warming up period, subjects began downhill running. The downhill protocol consisted of three 15-minute sessions with 5-minute rest intervals in seated position. Heart rate (using Polar heart rate monitor), and RPE (for cardiorespiratory and lower limbs, separately) were recorded every 5 minutes. Similar protocols have been successfully utilized to induce DOMS in young and older adults [7,11,27].

Anthropometric assessment. Height (± 0.1 cm) and body weight (± 0.1 kg) were measured using a physician's balance scale. Body composition was assessed using the 7-site skinfold thickness technique [19,20].

Joint range of motions. A goniometer was used to assess the range of motions of knee (extension) and hip (extension and flexion) joints as indices of muscle stiffness. Each measurement was repeated twice and averaged for both left and right sides. The sites of goniometer were marked with a semi-permanent-ink pen to ensure good day-to-day repeatability. Hip flexion was tested while the subject was placed in the supine position with their knees bent over the edge of the treatment table. The subject was instructed to flex the knee to the chest, and hip flexion angle was assessed. The stationary arm of the goniometer was placed along the lateral midline of the pelvis; the axis of movement placed at the lateral aspect of hip aligned with the greater trochanter, and the moving arm was placed along the lateral midline of the femoral lateral condyle.

Hip extension was assessed while the subject was placed in the prone position. While the pelvis is stabilized, the subject raised their leg off the table. The stationary arm of the goniometer was aligned the lateral midline of the pelvis; the axis of movement was placed on the lateral aspect of the hip aligned with the greater trochanter and the moving arm placed along the lateral midline of the femur aligned with the femoral lateral condyle.

Knee extension was measured with the subject laying supine, with both knee and hip flexed. The opposite leg lied flat on the table throughout the examination. The subject actively extended the knee through the full range of motion until resistance was felt, while the hip was maintained at 90° flexion. The stationary arm of the goniometer was aligned along the femoral greater trochanter; the axis of movement placed at the lateral femoral condyle at the knee joint and the moving arm aligned with the lateral malleolus.

Visual analog pain scale. A validated visual pain scale (VAS) was used to determine the level of muscle soreness [9]. The scale was on a 10-point scale (0 being absence of soreness, 10 being worst imaginable soreness). Subjects were asked to rate the VAS at their quadriceps, calves, and glutes during walking in daily life. In addition, VAS of subject's legs was obtained when angles of hip flexion (VAS-hip flexion), hip extension (VAS-hip extension), and knee extension (VAS-knee extension) were measured.

Muscular strength. Maximum voluntary isometric forces of the dominant knee extensors were measured using the isokinetic dynamometry system (Cybex II, Cybex, Inc, Ronkonkoma, NY). Subjects were seated on the machine, fixed by belts for waist,

shoulders, and thigh. Maximum isometric muscular strength was measured by determining peak torque during knee extension contractions at 90° and 45° of knee angles. Subjects performed three maximum knee extension contraction each for knee angles with 60-second rests between trials. The average peak torque of the three trials was used for further analyses.

Blood samples. Blood samples (5 ml) were drawn from the antecubital vein by a certified phlebotomist. Plasma was separated by centrifugation for 15 minutes. All plasma samples stored at -80°C until biochemical analyses at a later date. Creatine kinase activity and myoglobin concentration, as indices of muscle damage, were analyzed using commercially available ELISA assay kits. Due to the budget constraints, these measurements were measured only in the older trained and young trained groups.

Statistical analyses

Changes in dependent variables of muscular damages over time were compared among three groups by a two-way ANOVA with repeated measures (time x groups). Scheffe's post-hoc analyses were performed when significance was achieved. P-values less than 0.05 were considered significant. Numeric data are expressed as means±SEM. All statistical analyses were performed using StatView (5.0; SAS Institute, Tokyo, Japan) software.

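### Only downhill running is rehearsed at visit 1, so baseline torque may be unpractised and the strength deficit from baseline understated

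*Combined protocol and SAP*

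**What the plan says.** Under Procedures, visit 1 has a health questionnaire, a familiarization portion and a VO2max test. The purpose of the familiarization is given in one sentence: "The familiarization portion was used to introduce the subjects to downhill running on treadmill". VO2max values then "were measured using a maximum exercise test". No strength test or strength practice is listed at that visit.

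Strength first appears at visit 2, at the end of the list of baseline measurements and directly before the damaging exercise: "muscular strength of their leg (maximum isometric contraction). Following the measurements, subjects performed downhill running". Strength is obtained again at visits 3, 4 and 5, which are 24, 48 and 72 hours after the run. Visits 1 and 2 are 3 to 7 days apart.

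The Muscular strength section describes isometric knee extension on a dynamometer at two knee angles: "Subjects performed three maximum knee extension contraction each for knee angles with 60-second rests between trials". On scoring it says: "The average peak torque of the three trials was used for further analyses". It mentions no practice contractions, stability criterion or reliability figure.

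All three groups run downhill. The Statistical analyses section specifies a two-way repeated-measures ANOVA (time x group) at P<0.05, with no provision for a retest effect.

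**The concern.** A maximal voluntary contraction depends on effort and skill, and scores can rise once a subject has done the test. On the schedule as written, visit 2 may be the first exposure, whereas each post-exercise test follows at least one earlier session. A practice gain would then be added to every post-exercise value but not to baseline. It would act in the same direction as recovery and at the same visits. With one baseline and no unexercised group, nothing between visits separates the two.

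The study concerns recovery from strenuous exercise, and torque is its only strength measure. Creatine kinase and myoglobin were assayed only in the two trained groups (Blood samples), so comparisons with the sedentary group rest on torque, soreness and range of motion. The main thing at stake is a conclusion that strength is back to baseline when it is not. A secondary risk is a false time x group interaction if some groups gain more from practice than others.

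**Working it through.** The plan has no power calculation or expected effect to reproduce. The schedule is taken from the documents. The true deficits, practice gains, SDs and equal group sizes below are all assumptions.

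**1. Deficit from baseline.** For true deficit d and proportional practice gain g at every post-exercise visit, observed deficit = 1 - (1 - d)(1 + g). For example, d = 5% and g = 5% give 1 - 0.95 x 1.05 = 0.25%.

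| True deficit (assumed) | g = 2% | g = 5% | g = 10% |
|---|---|---|---|
| 15% (24 h) | 13.3% | 10.75% | 6.5% |
| 10% (48 h) | 8.2% | 5.5% | 1.0% |
| 5% (72 h) | 3.1% | 0.25% | 4.5% above baseline |

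Every deficit is understated. At a 5% gain, incomplete recovery at 72 h looks complete.

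**2. Slope from 24 to 72 h.** A true recovery of 15 - 5 = 10 points is observed as 10 x (1 + g), which is 10.2, 10.5 or 11.0 points. A constant gain moves the level much more than the slope.

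**3. Group contrast.** With equal gains, a true 5-point gap becomes 5 x (1 + g), or 5.1 points at 2% and 5.25 at 5%, so the gain nearly cancels. With unequal gains and the same true deficit, the false gap is (1 - d)(gA - gB). For gains of 5% and 2% this is 0.85 x 3 = 2.55 points at 24 h and 0.95 x 3 = 2.85 at 72 h. For 8% and 2% it is 5.1 and 5.7 points.

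**4. Time x group test.** Assume 13 per group (39/3), identical true deficits, within-subject SD of 5 or 8 points, and a gain in points added to visits 3-5. The interaction F has 2 x 3 = 6 and 36 x 3 = 108 degrees of freedom. Its noncentrality is 13 x S/SD², where S is the sum of squared group deviations in gain times 0.75. The 0.75 is the sum of squares of the visit pattern 0, 1, 1, 1 about its mean.

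- Gains 2/2/5 (mean 3): S = (1 + 1 + 4) x 0.75 = 4.5. Noncentrality is 2.34 (SD 5) or 0.91 (SD 8), and rejection is 16% or 9%.
- Gains 2/2/8 (mean 4): S = (4 + 4 + 16) x 0.75 = 18. Noncentrality is 9.36 or 3.66, and rejection is 58% or 23%.
- Equal gains: S = 0, and rejection is the nominal 5%.

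Simulation of the same model gave 17%, 9%, 57% and 24% for the four unequal cases, in agreement. In both unequal scenarios the two trained groups have the same gain (2 points), so the older-trained versus young-trained comparison stays at its nominal level.

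**The case against.** The strongest objection is that this argues from silence. The protocol is short, and practice contractions may have been done without being reported. That stands, and it is why the point is worded as something that may have happened.

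A reader might infer that the age comparison, older trained versus young trained, is contaminated. The documents do not support this. Equal gains nearly cancel, and nothing suggests that the two trained groups would learn the test differently. Even for the sedentary group, unequal gains are only possible. The trained subjects were mainly runners, and nothing shows that they had more experience of maximal dynamometry. The rejection rates of 9% to 58% rest wholly on assumed gains and SDs.

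A reader might also infer that the rate of recovery between 24 and 72 hours is inflated. Under a constant gain it hardly changes; the affected quantity is the distance from baseline.

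Averaging three trials might be read as a further source of bias. The same mean is used at every visit, so this is secondary. The six baseline contractions also give some practice within that session, and the separate trials allow a partial check. Torque is not named as a primary outcome, and soreness and range of motion are also described for all groups.

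What remains is the gap in the schedule: no rehearsal of an effort-dependent test, one baseline, and no group in which to measure a retest effect.

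**Conclusion.** The point holds as a limit on statements about strength deficit from baseline and time of return to baseline. The direction of bias follows from the schedule if baseline was the first exposure and scores rise with practice; its size is unknown. For assumed gains of 2% to 10%, a true 5% deficit at 72 hours would read as anything from 3.1% below to 4.5% above baseline. The point does not show that the time x group result is wrong, that any age effect is an artefact, or that the 24-72 hour slope is materially distorted. Biomarkers are not affected. It is worth correcting because the remedy is cheap and the between-visit data cannot separate practice from recovery afterwards.

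**What to change.** Add to Procedures that at visit 1 every subject practises the full strength test, at both knee angles, with the same positioning, number of contractions and rests. Place it so that it does not fatigue subjects for the VO2max test, for example after that test with adequate rest, because VO2max sets the downhill speed. Discard the practice values and keep visit 2 as baseline.

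The cost is one sentence, about 10 minutes and six isometric contractions at an existing visit. These fall at least 3 days before baseline, outside the protocol's own 48-hour restriction on strenuous exercise.

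The text is in the past tense. If testing is complete, no such sentence should be added unless practice took place. Instead:

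- state whether subjects practised on the dynamometer before visit 2;
- compare trials 1 to 3 at baseline, by angle and group, for within-session improvement;
- repeat the torque analysis with best-of-three peak torque as a sensitivity analysis;
- report the possible practice effect as a limitation, and limit conclusions about full strength recovery accordingly.

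This needs only the individual trial values. It can reveal learning within the baseline session but cannot rule out learning between visits.

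### Repeated-measures ANOVA on four time points states no sphericity correction; if sphericity fails, the nominal 5% time x group test plausibly runs at about 6-8% for soreness and 6-9% for the enzymes

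*Combined protocol and SAP*

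**What the plan says.** The Statistical analyses section says that changes in the muscle-damage variables over time were compared between the three groups by a "two-way ANOVA with repeated measures (time x groups". It adds that "Scheffe's post-hoc analyses were performed when significance was achieved" and that "P-values less than 0.05 were considered significant". It names the software package but not which of its p-values is used. It mentions no sphericity test, epsilon correction, multivariate test or mixed model.

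The rest of the design comes from other sections:

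- **Time points.** Under Procedures, baseline is taken at the second visit and follow-up at 24 hours (the third visit), "48 hours post (the fourth visit) and 72 hours post (the fifth visit". That makes four levels of time.
- **Soreness.** Under Visual analog pain scale: "The scale was on a 10-point scale (0 being absence of soreness, 10 being worst imaginable soreness". Under Downhill running: "Similar protocols have been successfully utilized to induce DOMS in young and older adults".
- **Enzymes.** Under Blood samples, for creatine kinase and myoglobin: "these measurements were measured only in the older trained and young trained groups".
- **Numbers.** Under Subjects, 39 people in three groups. The split is not given.

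**The concern.** With two time points sphericity is trivial. With four, the within-subject factor has 3 degrees of freedom, and the uncorrected F tests for time and time x group are valid only if the six pairwise between-visit differences share one variance. When they do not, the tests reject a true null too often.

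Three features of this design make equal variances unlikely for some outcomes:

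- Soreness should bunch near 0 before the run and spread out after it.
- Creatine kinase and myoglobin are taken as indices of damage, so their spread is likely to grow after the run.
- For any outcome, correlations may decay over days, which breaks sphericity even when SDs are equal.

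Time x group is the test of whether recovery differs between the groups, which is the question in the trial's title. It also opens the Scheffe comparisons, so an inflated F starts post-hoc testing too often. The main effect of time matters less, because a run meant to induce soreness makes a true null there implausible.

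**Working it through.** **Inputs from the documents:** significance threshold 0.05; N = 39; three groups; k = 4 time points; enzymes in two groups only.

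**Assumptions:** 13 per group (39/3), so 26 for the enzymes; SDs and correlations by visit as listed; one covariance matrix common to all groups.

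**Degrees of freedom for time x group:** (k-1)(G-1) and (k-1)(N-G).
- Three groups: 3 x 2 = 6 and 3 x 36 = 108; 5% critical value of F(6,108) = 2.18.
- Two groups: 3 x 1 = 3 and 3 x 24 = 72; 5% critical value of F(3,72) = 2.73.

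**Departure from sphericity.** Let A be the 3 x 3 covariance matrix of orthonormal contrasts among the four visits. Then epsilon = (tr A)² / [3 tr(A²)], which lies between 1/3 and 1, with 1 meaning sphericity. The variance of a between-visit difference is s_i² + s_j² - 2 r s_i s_j. In the enzyme case with SDs 1/4/2/1.5 and all correlations 0.7:
- baseline to 24 h: 1 + 16 - 2(0.7)(1)(4) = 11.4
- baseline to 72 h: 1 + 2.25 - 2(0.7)(1)(1.5) = 1.15

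This tenfold ratio gives epsilon 0.49.

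**Box approximation.** Size = P{F(eps·df1, eps·df2) > 5% critical value of F(df1, df2)}. At epsilon 1 it returns the plan's own 5.0%.

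| epsilon | three groups | two groups |
|---|---|---|
| 1.0 | 5.0% | 5.0% |
| 0.9 | 5.7% | 5.7% |
| 0.8 | 6.6% | 6.4% |
| 0.7 | 7.6% | 7.2% |
| 0.6 | 8.7% | 8.2% |
| 0.5 | 10.1% | 9.2% |
| 1/3 (lower bound) | 12.7% | 11.1% |

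**Null simulation of time x group.** There were 40,000 trials per normal case. The standard error at 5% is √(0.05 x 0.95/40,000), about 0.1 percentage point.

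| Case (SDs at 0/24/48/72 h; correlation) | Groups | Uncorrected | Greenhouse-Geisser |
|---|---|---|---|
| Even: equal SDs; exchangeable 0.6 | 3 | 4.9% | 4.4% |
| Even: equal SDs; exchangeable 0.6 | 2 | 5.1% | 4.3% |
| Equal SDs; AR(1) 0.5 | 3 | 6.1% | 4.6% |
| Equal SDs; AR(1) 0.8 | 3 | 7.0% | 4.8% |
| Soreness 0.3/2/2/1.5; AR(1) 0.6 | 3 | 5.7% | 4.5% |
| Soreness 0.5/2/2.5/1.5; AR(1) 0.6 | 3 | 6.4% | 4.7% |
| Soreness 0.3/2/2/1; exchangeable 0.5 | 3 | 6.8% | 4.7% |
| Soreness 0.2/2/2/1; AR(1) 0.7 | 3 | 7.4% | 5.0% |
| Enzyme 1/3/2/1.5; exchangeable 0.6 | 2 | 7.1% | 4.9% |
| Enzyme 1/5/3/2; exchangeable 0.6 | 2 | 7.8% | 4.9% |
| Enzyme 1/4/2/1.5; exchangeable 0.7 | 2 | 8.7% | 5.0% |

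Epsilon is 0.71-0.88 across the soreness rows and 0.49-0.69 across the enzyme rows.

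**Variations** (20,000 trials each):
- Soreness rounded and floored to 0-10: 5.9-7.7% uncorrected, 4.6-5.1% corrected.
- Lognormal enzymes on the raw scale (log SD 0.4-0.7): 6.3-7.6% uncorrected, 3.8-4.3% corrected.
- Unequal splits: soreness 5.8-7.5% (10/13/16, 9/15/15, 15/12/12); enzymes 7.8% (10/17, 12/15).

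**Second, separately chosen set of covariances:** soreness 5.9-8.4%; lognormal enzymes 6.7-8.8%; normal enzymes 7.8% and 9.2%, with one extreme case (epsilon 0.38) at 10.1%.

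**The case against.** Several points can be made against this concern.

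- **The size rests on assumed covariances.** This stands. The documents show only that no correction is stated. One may have been applied without being reported, and under even spread there is no inflation.
- **The model may have three levels, not four.** The plan speaks of changes over time, which could mean changes from baseline at three visits. On that reading the four normal soreness cases have epsilon 0.94-1.00 and run at 4.7-5.4%, so the soreness inflation essentially disappears. The normal enzyme cases still run at 5.8-6.9%. Raw values at all four visits is the more usual reading of a time x groups repeated-measures ANOVA, but the text does not settle it.
- **The power cost may exceed 2-3 points.** Under non-sphericity the gap is wider: 57.0% vs 52.8% and 48.5% vs 42.2% in two soreness cases, 64.1% vs 52.2% for normal enzymes, and 63.3% vs 48.6% for lognormal enzymes. Much of this gap is the uncorrected test's inflated size. Some is real, because the correction is conservative (3.8%) in that lognormal case.
- **Greenhouse-Geisser does not repair unequal spread between groups.** This is true. With a 9/15/15 split and SDs 1.5 times larger in the smallest group, the soreness cases run at 10.1-11.3% uncorrected and 8.3-8.9% corrected. Enzymes at 10/17 go from 11.2% to 8.0%. That is a separate problem, and the correction still lowers the error.
- **The excess is modest, and no stated decision is shown to turn on it.** The first part is fair and limits how much weight the point should carry.

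**Conclusion.** The concern holds. Run as written, the plan's only omnibus test is anti-conservative whenever sphericity fails, and the design gives good reason to expect failure for soreness and the enzymes. Under the assumptions above, the nominal 5% time x group test runs at about 6-8% for soreness and 6-9% for the enzymes. The excess is modest for soreness and somewhat larger for the enzymes. These are rates per outcome and not upper limits.

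Strength and range of motion have no floor at 0, so their tests stay near 5% if spread and correlations are even. Serial decay alone would take them to about 6-7%.

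Confidence is medium. The omission is plain in the text, but its size depends on covariances that the documents do not give and on analysing four time levels. The point should be fixed; it does not by itself undermine the study.

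**What to change.** State in the Statistical analyses section that inference for time and time x group is based on Greenhouse-Geisser-corrected p-values for every outcome. The correction estimates epsilon from the data, so no prior covariance is needed. The same sentence should say whether the model uses values at four visits or changes at three. A mixed model with unstructured covariance is an optional alternative, not needed for this point.

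The cost is one sentence and slightly larger p-values. The text is in the past tense, so if uncorrected results already exist the p-values must be recomputed; no new data are needed. Where sphericity holds, size falls to 4.3-4.4%. Power then falls from 59.2% to 57.1% with three groups and from 57.6% to 54.8% with two (equal SDs, exchangeable 0.6, one group shifted by 0.8, 0.8 and 0.4 SD at 24, 48 and 72 h). For lognormal enzymes on the raw scale the corrected test is conservative, at 3.8-4.3%.

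### If Scheffe is used to compare 24, 48 and 72 h with baseline, it is stricter than those three comparisons need; adjusted baseline contrasts with intervals would be a cheap improvement

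*Combined protocol and SAP*

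**What the plan says.** The Statistical analyses section sets out a "two-way ANOVA with repeated measures (time x groups" factors), states its target as "Changes in dependent variables of muscular damages over time were compared among three groups", and adds one follow-up, in which Scheffe's "post-hoc analyses were performed when significance was achieved". The threshold is given by "P-values less than 0.05 were considered significant". Outcomes are taken at a baseline visit and then, in the Procedures paragraph, at "24 hours post (the third visit), 48 hours post (the fourth visit) and 72 hours post (the fifth visit"). That makes four visits, three of them after the downhill run.

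The Subjects paragraph gives the size ("A total of 39 healthy men and women were studied") and three groups, without group sizes. The Blood samples paragraph limits creatine kinase and myoglobin to the two trained groups.

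The section does not say whether Scheffe is applied to visits, to groups or to group-by-visit cells. It does not name comparisons with baseline, and it gives no confidence intervals. Nowhere does the document define recovery or say how it would be dated.

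**The concern.** The title asks about rate of recovery. The natural way to describe recovery is to compare each post-exercise visit with the subject's own baseline, and Scheffe is the only tool the plan offers for locating a difference after a significant ANOVA. Scheffe controls error over every possible contrast among the four visit means. A reader of a recovery study needs three of them.

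Some adjustment is needed, because with four visits a significant overall F does not by itself protect the individual comparisons. Protection beyond the three needed comparisons is paid for in power. The price falls on modest residual changes, which is what one might expect at 48 and 72 h. The blood markers are not exempt: they have two groups but still four visits.

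A strict test is also not the cautious choice in a recovery study, since missing a real residual change leaves the impression that there is none.

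**Working it through.** The plan states no sample-size calculation, power, effect size or SD, so there is no figure to reproduce.

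**Inputs from the document:** 39 subjects, three groups, four visits, two groups for the blood markers, significance at 0.05. **Assumptions:** 13 subjects per group (39/3), so 26 with blood markers; two-sided tests; pooled within-subject error and sphericity; effects expressed as d = mean change / SD of change.

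**Error df:** (visits − 1) × (subjects − groups). All outcomes: 3 × (39 − 3) = 108. Blood markers: 3 × (26 − 2) = 72.

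**Critical |t| for a comparison with baseline, df 108**

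- Scheffe over four visits: √(3 × F0.95(3,108)) = √(3 × 2.689) = 2.84
- Bonferroni for three: t(1 − 0.05/6; 108) = 2.43
- Dunnett, by simulation with correlation 0.5 from the shared baseline: 2.38

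The two-sided level per comparison is 0.0054, 0.0167 and 0.019 respectively. The error rate over the three comparisons together is 0.015, 0.044 and 0.050. The smallest difference that reaches significance is 2.84/2.38 = 1.19 times as large with Scheffe as with Dunnett.

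**Blood markers, df 72:** Scheffe √(3 × 2.732) = 2.86; Bonferroni 2.45; Dunnett 2.40. The numerator df is still 3 because it comes from the visits, not the groups.

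**Power,** from the noncentral t with noncentrality d√n (for d = 0.7: 0.7 × √13 = 2.52; 0.7 × √39 = 4.37):

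| Comparison with baseline (df 108) | d | Scheffe | Dunnett |
|---|---|---|---|
| Within one group, n = 13 | 0.5 | 16% | 29% |
| | 0.7 | 38% | 56% |
| | 0.8 | 52% | 69% |
| All subjects, n = 39 | 0.5 | 61% | 77% |
| | 0.7 | 93% | 98% |
| | 0.8 | 98% | 99.5% |

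Bonferroni lies close to Dunnett: 27, 54 and 67% for n = 13. For the blood markers over an assumed 26 subjects, power at d = 0.5, 0.7 and 0.8 is 38, 76 and 88% with Scheffe against 56, 88 and 95% with Dunnett.

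**Effect on recovery, only if non-significance were read as recovered:** at d = 0.7 in a group of 13, a group that still differs would be called recovered 100 − 38 = 62% of the time with Scheffe and 100 − 56 = 44% with Dunnett.

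**Pooled error.** In one simulated case with no true change, three groups of 13 and assumed SDs of 0.3, 1.5, 1.2 and 0.6 over the four visits, the error rate per comparison at 24, 48 and 72 h was 0.020, 0.004 and about 0 with pooled Scheffe. It was 0.046, 0.012 and about 0 with pooled Bonferroni, and 0.017, 0.018 and 0.016 with visit-specific paired errors and Bonferroni. If variances differ across visits, the error term can matter as much as the choice of adjustment.

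Visit-specific errors have their own price. Pooled over the three groups (39 − 3 = 36 df) the Bonferroni critical value is 2.51, and power for n = 13 at d = 0.5, 0.7 and 0.8 is 25, 51 and 65%. Estimated from one group alone (12 df) it is 2.78, and power is 21, 43 and 56%.

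**The case against.** The strongest objection is that the plan never says Scheffe is applied across visits. The comparison it names is among groups, and a test cannot be too strict for a purpose the text does not assign to it. This stands, and it makes the point conditional. A reader might go further and infer that Scheffe runs over all 12 group-by-visit cells, where the critical value would be 4.55. Nothing in the text supports that, so no weight is placed on it. Between the two blood-marker groups Scheffe equals the ordinary t test (2.064 for both), so any penalty there concerns visits only.

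A reader might also infer that the trial will date recovery too early. The documents do not support this as stated, because they contain no rule for recovery and do not treat a non-significant difference from baseline as a return to it. Such a rule would be unsafe under any post-hoc test: Dunnett would still miss a 0.7 SD change 44% of the time.

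A third tempting inference is that the harm is greatest in the more variable group and so distorts comparisons of recovery between groups. With a pooled error term this fails. In a simulation with group SDs in the ratio 0.7:0.7:1.5 and a true change of 0.7 pooled SD in each group, the more variable group was flagged more often (43% against 34%).

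Finally, Scheffe is valid, and the size of the loss depends on effects and SDs that the plan does not give. With all 39 subjects and a large change it almost vanishes. All of this is right and limits the point. It does not show that Scheffe suits three comparisons with baseline.

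**Conclusion.** The point holds conditionally, as a cheap improvement. If Scheffe is the test used to compare 24, 48 and 72 h with baseline, it works at a family error rate of about 0.015 rather than 0.05. At moderate changes it costs roughly 13 to 18 percentage points of power within a group of 13 (d from 0.5 to 0.8). Over all 39 subjects the cost is about 16 points at 0.5 SD, 4 to 5 at 0.7 SD and 1 to 2 at 0.8 SD. The same holds across visits for creatine kinase and myoglobin.

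The critical values rest on 108 and 72 error df; the latter assumes 26 subjects with blood markers. The power figures also assume equal groups, sphericity and the listed effect sizes. No claim is made that recovery will in fact be misdated.

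**What to change.** In the Statistical analyses section, replace Scheffe for visit comparisons with three pre-stated changes from own baseline within each group, at 24, 48 and 72 h, adjusted by Bonferroni, Holm or Dunnett. Visit-specific paired errors are preferable; pooling them over groups keeps more power than estimating them in each group alone. Report every mean change with its adjusted 95% interval, whether or not it is significant.

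State that recovery is not inferred from non-significance. It is claimed only when the interval excludes a pre-stated meaningful residual change: a loss for strength and range of motion, a rise for soreness, creatine kinase and myoglobin.

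The cost is a few sentences of analysis text and no new data. Unplanned contrasts among visits would no longer be covered, and one margin must be stated and justified for each outcome. The document is written in the past tense, so if the results have already been seen, these contrasts and margins should be labelled as chosen afterwards.
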